5.6 Project Management and Data Monitoring

5.6.1 Project Management

The project will be sponsored by South Tees Hospitals NHS Foundation Trust.

Each site will have a site PI who will be responsible locally for the study and where possible an Associate PI (API) who will be a trainee surgeon or another appropriate member of the research team. APIs will be encouraged to register with the NIHR API scheme.

YTU is undertaking the duties formally delegated by the trial Sponsor.

The trial manager at YTU will be responsible for all aspects of trial management. They will be supported by a trial co-ordinator(s), who will be responsible for the day-to-day support of trial sites, coordinate recruitment, data handling, and the management of the administrative trial team. The team at YTU will meet on a regular basis during the study and will work closely with the co-chief investigators (CIs), particularly at the start of the project and during the internal pilot of the study, including regular teleconferences to ensure that all aspects of preparation of study material, study site setup and the start of recruitment progress smoothly. They will keep in close contact via email and telephone throughout.

The primary responsibility for monitoring the safety of participants in clinical trials lies with the trial Sponsor. Data monitoring will be undertaken by the Trial Management Group (TMG), TSC, and a Data Monitoring Committee (DMC), on behalf of the Sponsor and Funder. The project will also be monitored by the Sponsor for whom a representative will be invited to attend the TMG and TSC meetings. The minutes/records of these meetings will be stored at YTU and will be shared with the sponsor on a routine basis.

5.6.2 Trial Management Group (TMG)

A Trial Management Group (TMG) has been established to monitor the day-to-day management (e.g. protocol and ethics approvals, set up, recruitment, data collection, data management) of the study. Chaired by the Chief Investigator, membership will include the co-applicants, coinvestigators, members of YTU (trial manager, statistician) and other research staff on the project. Throughout the project there will be regular teleconference contact supplemented by face-to-face meetings where required (at least annually). Frequency of meetings will vary depending on the stage of the trial but at least monthly during the early stages and pilot.

5.6.3 Trial Steering Committee (TSC)

Independent oversight of the study will be conducted by the Trial Steering Committee (TSC) which will provide overall supervision for FLARE on behalf of the Sponsor and Project Funder and ensure that the project is conducted to the rigorous standards set out in the UK Policy Framework for Health and Social Care Research and the Guidelines for Good Clinical Practice. The TSC will monitor the progress of the trial and provide independent advice. This committee comprises of an Independent Chair, a public contributor, and the Chief Investigator. A Sponsor representative will also be invited to attend the TSC meetings. Other study collaborators may also attend the meeting

FLARE Protocol 17.03.2023 Version 1.1 Page 35

with the agreement of the Chair. The TSC will meet at least annually and will work to a Charter which has been agreed.

5.6.4 Data Monitoring Committee (DMC)

The study will be regularly reviewed by the independent Data Monitoring Committee (DMC) comprising of independent clinicians and health service researchers with appropriate expertise. The role of the DMC is to review accumulating trial data and advise the sponsor (directly or indirectly) on the future management of the trial.

The DMC will meet at least annually or more frequently if the committee requests, to provide project oversight to the trial. The DMC will review safety and efficacy data as well as quality and compliance data. The DMC will review all serious adverse events which are thought to be treatment related and unexpected. The independent members of the DMC committee will be allowed to see unblinded data.

The DMC will adopt a DAMOCLES charter [40] which will define its terms of reference and responsibilities in relation to oversight of the trial.

6. Safety Monitoring

6.1 Definitions

An adverse event (AE) will be defined as the following: any untoward medical occurrence in a trial participant to whom a research treatment or procedure has been administered (intervention or control) and which does not necessarily have a causal relationship with the treatment. For the purposes of FLARE, we will only collect AE data for events that are related to the original finger injury and unexpected.

Complications, which might be expected with this condition and treatments, are detailed in Table 9: Expected complications associated with flexor tendon repair surgery(section 6.2) should not be reported as an adverse event. These are well known complications of surgery of which the specialist clinical care teams will be experienced in managing. These complications however will be recorded in the FLARE CRFs.

Where repeated adverse events of similar type are observed, these will be discussed with the DMC and will be onward reported to Sponsor and REC should concerns be raised in relation to the type of event and/or frequency observed.

A serious adverse event (SAE) will be defined as any untoward occurrence that:

- Results in death. •
- Is a life-threatening event (that is it places the participant, in the view of the Investigator, at • immediate risk of death).
- Requires unplanned hospitalisation or prolongation of existing hospitalisation (unplanned • refers to emergency hospitalisations resulting in an inpatient stay; prolonged hospitalisation is deemed to be where a participant's stay is longer than expected).
- Results in persistent or significant disability or incapacity (substantial disruption of one's • ability to conduct normal life functions).
- Is another important medical condition.

Version 1.1

Important medical events that may not be immediately life-threatening, result in death or hospitalisation but may jeopardise the participant or may require intervention to prevent one of the outcomes listed in the definition of an SAE will also be considered serious.

In the context of this study, SAEs will only be reported to YTU if they appear to be related to the original injury or an aspect of taking part in the study.

Other than for fatalities, this procedure does not apply to any other SAEs which may occur during the trial which are unrelated to original injury or the trial procedures.

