6.2 Collection, Recording and Reporting of Adverse Events

An appropriate member of the research team will record all directly observed AEs and all AEs reported by the trial participant up to six months following their trial treatment.

In addition, sites should follow their own local procedures for the reporting of any adverse events linked to clinical care.

All AEs requiring reporting will be recorded on an (S)AE form or REDCap data collection tool and will be reported to YTU according to the agreed timelines.

The severity and likely relationship to study treatments of any adverse events will be documented by the designated site clinician.

An event is defined as 'related' if the event was due to the administration of any research procedure. Whereas an 'unexpected event' is defined as a type of event not listed in the protocol as an expected occurrence.

All non-serious AEs whether expected or not, should be recorded in the participant's medical notes.

Related and unexpected AEs will be recorded on the study AE data collection tool by the research staff and sent to YTU within an agreed timescale (usually five days). SAEs should be notified to the Principal Investigator and to YTU within 24 hours of the research staff or clinical team becoming aware of the event.

At the time of reporting, the PI or delegated clinician will be asked to record an assessment of causality (to trial treatment) selecting an option from the list below:

- Definitely related- there is clear evidence to suggest a causal relationship, and other possible • contributing factors can be ruled out.
- Probably related- there is evidence to suggest a causal relationship, and the influence of other factors is unlikely
- Possibly related- there is some evidence to suggest a causal relationship (e.g. the event • occurred within a reasonable time after administration of the trial procedures). However, the influence of other factors may have contributed to the event (i.e. the participant's clinical condition, other concomitant events).
- Unlikely to be related- there is little evidence to suggest there is a casual relationship (e.g. • the event did not occur within a reasonable time after administration of the trial procedures). There is another reasonable explanation for the event (e.g. the participant's clinical condition, or other concomitant treatments).
- Unrelated- there is no evidence of any causal relationship.

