17.3.7 Adverse Events

Table 26: Number of non-serious adverse events per participant presented overall and by treatment group.

	Intervention	Control	Overall
	N=	N=	N=
One or more NSAEs, N (%)			
Yes			
No			
Number of NSAEs per participant, N (%)			
0			
1			
Days between randomisation and onset of			
NSAE			
Ν			
Mean (SD)			
Median			
Min, Max			
Study action taken, N (%)			
None			
Study treatment halted			
Discontinued study			
Relationship to study treatment, N (%)			
Not related			
Unlikely to be related			
Possibly related			
Probably related			
Related			
Expectedness, n (% of those possibly,			
probably or definitely related)			
Yes			
No			

Table 27: Number of serious adverse events per participant presented overall and by treatment group.

	Intervention	Control	Overall
	N=	N=	N=
One or more SAEs, N (%)			
Yes			
No			
Number of SAEs per participant, N (%)			
0			
1			
2			
3			

Days between randomisation and onset of		
SAE		
N (% data available)		
Mean (SD)		
Median		
Min, Max		
Study action taken, N (%)		
Study treatment interrupted/halted		
Discontinued study		
None		
Relationship to study treatment, N (%)		
Not related		
Unlikely to be related		
Possibly related		
Probably related		
Related		
Expectedness, n (% of those possibly,		
probably or definitely related)		
Yes		
No		

Table 28: Non-serious adverse event details by site and allocation.

Participant ID	Site ID	Allocation	Onset date	Action Taken	Related	Outcome	Description

 Table 29: Serious adverse event details by site and allocation

Participant ID	Site ID	Allocation	Onset date	Action Taken	Related	Outcome	Description

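### Protocol 6.1 and 6.2 use different meanings of 'related', so an unexpected, non-serious event caused by the trial surgery but not by the injury is left out by one section and required by the other

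*Protocol*

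**What the plan says.** Protocol 6.1 first defines an adverse event (AE) broadly, as any untoward occurrence in a participant given a research treatment or procedure in either arm, whether or not caused by it. It then narrows what is collected: "For the purposes of FLARE, we will only collect AE data for events that are related to the original finger injury and unexpected". Expected complications, listed in Table 9, are not reported as AEs but are recorded on the case report forms (CRFs). Repeated AEs of a similar type are to be discussed with the DMC. Serious adverse events (SAEs) go to the trials unit only "if they appear to be related to the original injury or an aspect of taking part in the study".

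Protocol 6.2 works from another definition: "An event is defined as 'related' if the event was due to the administration of any research procedure". It then gives the operative duty: "Related and unexpected AEs will be recorded on the study AE data collection tool by the research staff and sent to YTU", usually within five days. The investigator or a delegated clinician "will be asked to record an assessment of causality (to trial treatment) selecting an option from the list below". The same section says that staff will "record all directly observed AEs and all AEs reported by the trial participant up to six months following their trial treatment".

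SAP 13.8 summarises AEs and SAEs descriptively by event type, expectedness and relatedness to study treatment. The example tables in SAP 17.3.7 (Table 26 for non-serious events, Table 27 for serious events) have five rows under "Relationship to study treatment, N" and a Yes/No split for expectedness.

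**The concern.** Relatedness decides which non-serious events enter the trial database, and the two sections attach it to different things: the finger injury in 6.1, the research procedure in 6.2. Both sentences are operative, and a site cannot follow both.

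The direction of the mismatch matters. Participants are randomised in theatre, after the injury, so randomisation should balance events due to the injury alone. Events due to the treatment are the ones that could differ between arms, and these are what 6.1 omits if followed literally. Protocol 4.10.2 records that patients consulted about the trial were concerned about the safety of not repairing both tendons, so an unforeseen and unlisted consequence of treatment is something the trial would want to see. The rule that sends repeated similar AEs to the DMC can act only on events that were collected.

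**Working it through.** No arithmetic applies; the check is a comparison of texts. Four kinds of event are traced through the rules in Protocol 6.1 and 6.2.

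| Event | Protocol 6.1 | Protocol 6.2 | Result |
|---|---|---|---|
| A. Unexpected, non-serious, caused by the trial surgery and not by the injury, not in Table 9 | Not collected | Record on the AE tool and send to the trials unit | Conflict |
| B. Unexpected, non-serious, due to the injury and not to any research procedure | Collected | Not 'related', so not required | Conflict, reversed |
| C. Serious, caused by the trial surgery | Reportable, because the SAE filter adds taking part in the study | Notify within 24 hours | No conflict |
| D. Complication listed in Table 9 | On the CRF, not as an AE | Not 'unexpected' | No conflict |

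**Can 6.1 be read so that A is included?** Only if 'related to the injury' also covers the treatment of the injury. The SAE sentence in 6.1 names the injury and trial participation as alternatives, and the sentence after it again separates the injury from the trial procedures. The protocol therefore treats them as different things, and its AE sentence has only the first.

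**Are there three meanings or two?** 'Research procedure' and 'trial treatment' in 6.2 are close, because the AE definition in 6.1 speaks of a research treatment or procedure in either arm. The real clash is injury against treatment or procedure.

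**Effect on SAP Table 26.**
- Expectedness: both filters require the event to be unexpected, so the 'Yes' row should be empty whichever section a site follows, apart from events reclassified when the Chief Investigator confirms expectedness.
- Relationship: causality is scored to treatment. Under the 6.1 filter, an event of type B enters and can be scored as not related. Under the 6.2 filter, type B is not required. What these rows contain therefore depends on the filter, and they are not empty by design.

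**Effect on SAP Table 27.** The SAE filter neither requires unexpectedness nor excludes events due to the injury alone, so no row is ruled out.

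**The case against.** The strongest reply is that little is lost.

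- The foreseeable harms of the repair, including re-rupture, adhesions, infection, stiffness, bow stringing and nerve injury, are in Table 9 and go on the CRFs. SAP 13.6 compares tendon rupture, deep and superficial infection, rehospitalisation and further surgery by logistic regression if there are at least 5 events per arm.
- Protocol 4.9.2 collects information on all complications and does not limit these to its examples. SAP Table 25 adds intra-operative complications and says that all complications will be reported. An unlisted surgical event may therefore reach the data by another route.
- Protocol 6.2 puts all non-serious AEs in the medical notes. Its instruction to record every AE can be read as that first tier, with a second tier for those sent to the trials unit, so it need not be a further contradiction.

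Most of this stands and limits the point. It does not remove it: SAP 7.2.11 describes the complications outcome in terms of expected complications, so the backstop is only partial, and the two AE rules still disagree.

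Three stronger readings are tempting, and the documents do not support them. A reader might infer that capture of treatment-caused events swings from none to all with the section followed; the complications route rules out so clean a contrast. A reader might infer biased AE comparisons; but allocation is stratified by site and site research staff are to be blinded, so a site's reading applies to both arms and costs completeness. A reader might infer that the 'not related' rows of Table 26 are zero by design; under 6.1 they are not.

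**Conclusion.** The contradiction is real and sits in the current text. It affects unexpected, non-serious events outside Table 9: those caused by the trial surgery and not by the injury, and the reverse. The consequence is incomplete and inconsistent capture across up to 40 sites, a weaker trigger for referring repeated events to the DMC, and a Table 26 whose relationship rows cannot be interpreted without knowing which filter was used. The primary outcome, the analysed complications and the reporting of serious events caused by the surgery are not affected.

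No number can be put on the events lost, because the documents give no rate for events of this kind. The conclusion assumes that the trial surgery counts as a research procedure under 6.2, which the AE definition in 6.1 supports, and that sites have no separate guidance that already settles the matter; none appears in the documents. The change is worth making because it is specific and cheap, and because 6.1 taken literally omits the unexpected events that the treatment could cause.

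**What to change.** 1. Reconcile Protocol 6.1 and 6.2 to one AE filter that includes unexpected events possibly, probably or definitely related to the trial treatment or procedures. Using the two-part SAE wording (the injury, or taking part in the study) for AEs as well would do this.
2. Keep the injury clause in the SAE filter; it should not be narrowed.
3. Record attribution to the injury in its own field, separate from the causality score for trial treatment.
4. In the SAP, state which filter generated Table 26 and that its expectedness 'Yes' row is expected to be empty by design. Make no such statement for the relationship rows or for Table 27.
5. Tell sites which rule applies and note the date of the change.

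The cost is a protocol wording amendment, one CRF field and slightly more AE forms. There is also a cost in continuity. The SAP was signed on 28 April 2025, and its recruitment figure note has the restarted pilot running from May 2024 to the end of April 2025. AEs before and after the change would be collected under different wording, so the report should give the date and, where useful, show the two periods separately.

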Once received, causality and expectedness will be confirmed by the Chief Investigator. SAEs that are deemed to be unexpected and related to the trial will be notified to the Research Ethics Committee (REC) and Sponsor within 15 days.

All such events will be reported to the Trial Steering Committee and Data Monitoring Committee at their next meetings. All participants experiencing SAEs will be followed up as per protocol until the end of the trial.

General surgical complications Deep wound infection Superficial infection Bleeding /haematoma Suture abscess Surgical site infection Rehospitalisation Delayed wound healing / wound dehiscence Unexplained pain Tourniquet related nerve injury **Anaesthetic-related complications** Myocardial infarction (MI) Block related nerve lesion Cerebrovascular accident (CVA) Venous thromboembolism (VTE) Local anaesthetic toxicity Complications specific to flexor tendon repair surgery Digital nerve injury / neuroma / numbness / **Tendon adhesions** altered sensation Re-rupture of tendon repair Cold intolerance Complex regional pain syndrome Bow stringing Joint stiffness Hand Therapy-related Complications Skin problems related to splint fitting

Table 9: Expected complications associated with flexor tendon repair surgery

7. Research Governance

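### Protocol 6.1 exempts Table 9 complications from adverse event reporting with no exception for serious ones; this contradicts the protocol's own SAE rules, and serious Table 9 events fall outside the DMC's stated SAE review

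*Protocol*

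**What the plan says.** Protocol 6.1 restricts adverse event collection at the outset: "we will only collect AE data for events that are related to the original finger injury and unexpected". It then says that the complications listed in Table 9 "should not be reported as an adverse event", and directs them to the CRFs instead. No wording brings a Table 9 event back into reporting if it is serious.

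Table 9 (in 6.2) is broad. Its anaesthetic group includes "Myocardial infarction (MI) Block related nerve lesion Cerebrovascular accident (CVA) Venous thromboembolism (VTE"). Its general surgical group includes "Surgical site infection Rehospitalisation Delayed wound healing". Its tendon-specific group includes "Re-rupture of tendon repair".

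The same section 6.1 goes on to define a serious adverse event by its consequences. One criterion is that it "Requires unplanned hospitalisation or prolongation of existing hospitalisation"; another is that it is life-threatening. None of the criteria depends on whether the event was expected. SAEs go to the trials unit if they appear related to the injury or to taking part. Section 6.2 sets a 24-hour deadline for SAEs and has the Chief Investigator confirm causality and expectedness once the report is in.

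On oversight, Protocol 5.6.4 says: "The DMC will review all serious adverse events which are thought to be treatment related and unexpected". REC and Sponsor notification in 6.2 uses the same two conditions. Section 6.2 defines an unexpected event as one whose type the protocol does not list as expected.

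**The concern.** A site with a serious Table 9 event has two instructions that cannot both be followed: do not report it as an adverse event, or send it as an SAE within 24 hours. If sites resolve this differently, the SAE dataset depends on local interpretation, and the comparison of SAEs by arm in SAP Tables 27 and 29 may be incomplete.

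This matters more here than in a trial where the listed complications are unrelated to the treatment contrast. Protocol 1.1 cites a comparative study in which repairing both tendons had a higher reoperation rate for rupture or adhesions. Protocol 4.10.2 records patients' concern about the safety of leaving one tendon unrepaired. Re-rupture and readmission are therefore plausible places for the arms to differ, in either direction, and they are among the events whose serious cases have no clear route to the DMC.

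**Working it through.** This is mainly a consistency check, so the rules are set side by side for a Table 9 event that is related and meets a seriousness criterion.

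| Rule | Where | Filter used | Result for a serious, related Table 9 event |
|---|---|---|---|
| AE collection | Protocol 6.1 | Related and unexpected | Not collected |
| Table 9 exemption | Protocol 6.1 | Event type listed | Not reported as an AE; goes on the CRF |
| SAE definition | Protocol 6.1 | Seriousness | Is an SAE |
| SAE reporting to trials unit | Protocol 6.1 | Relatedness | Reported |
| 24-hour deadline | Protocol 6.2 | Is an SAE | Applies |
| Expectedness check | Protocol 6.2 | Made after receipt | Presumes the report arrives |
| SAE summary | SAP 13.8, Table 27 | Expected yes/no | Presumes expected SAEs are in the data |
| DMC's stated SAE review | Protocol 5.6.4 | Related and unexpected | Outside |
| REC and Sponsor notification | Protocol 6.2 | Related and unexpected | Outside |

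**Step 1: the contradiction.** Take an unplanned emergency inpatient readmission related to the injury. It is a rehospitalisation, so the exemption says not to report it as an adverse event. It also meets the hospitalisation criterion and the relatedness filter, so 6.1 and 6.2 make it an SAE due within 24 hours. Rows 1 and 2 give one answer and rows 3 to 7 give the other. Rehospitalisation is the sharpest case because it largely restates a seriousness criterion and is not a diagnosis.

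**Step 2: the DMC and REC filters.** Unexpectedness depends on type alone, so every Table 9 event is expected however severe it is. The last two rows therefore exclude it whichever answer is taken in Step 1. This comes from 5.6.4 combined with the definition in 6.2, not from the exemption sentence itself.

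**Step 3: scale.** The plan gives no expected number of such events. The denominator is the target of 310, which reproduces, taking a true difference of zero: per arm n = 2(1.960 + 1.282)² × 17² / 7² = 123.9, rounded up to 124; 2 × 124 = 248; 248 / (1 − 0.20) = 310. The only related rate in the documents is the re-repair rate in Protocol 1.2, described as reaching 17%. The lower rates below are assumptions.

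| Assumed re-rupture or re-repair rate | 310 × rate | Participants |
|---|---|---|
| 2% | 6.2 | about 6 |
| 5% | 15.5 | about 16 |
| 10% | 31.0 | 31 |
| 17% (highest cited) | 52.7 | about 53 |

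These are participants with the event. Only those meeting a seriousness criterion are affected by the contradiction, and the documents do not give that fraction.

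**The case against.** The strongest reply is that the exemption was never meant to cover SAEs. It speaks of adverse events and precedes the SAE definition; the SAE filter uses relatedness only; 6.2 treats non-serious events as a separate class; and both the post-receipt expectedness check and SAP Table 27 assume that expected SAEs arrive. This is a fair reading. A reader might infer that the protocol definitely takes serious Table 9 events out of 24-hour reporting. The documents do not support that as a statement of fact: it is one of two readings.

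The reply does not remove the conflict. The adverse event definition in 6.1 covers any untoward medical occurrence, so an SAE is a kind of adverse event, and a list containing rehospitalisation is hard to read as confined to non-serious events. The expectedness row in Table 27 is also only suggestive. Table 26, for non-serious events, carries the same row although 6.1 collects only unexpected ones.

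The second reply is that nothing is lost, and most of this stands. Complications go on the CRFs. SAP Table 25 shows them by arm from one week to six months, with named rows for re-rupture, MI, CVA and VTE and a note that all complications will be reported. SAP 13.6 models tendon rupture, rehospitalisation and further surgery if there are at least 5 events per arm. A reader might infer that these events surface only on forms filled in at scheduled visits. SAP 8.1 lists an additional surgery form not tied to a visit, and SAP section 5 adds a six-month record review. What these routes lack is a stated reporting deadline.

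The third reply is that the DMC reviews safety and efficacy data generally, may see unblinded data and can meet more often than annually. That stands too, and its charter is not among the documents. But no text says that Table 9 complications go to it. The 6.1 provision for discussing repeated similar events with the DMC is written for adverse events, the class from which Table 9 events have been removed.

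**Conclusion.** The point holds as a contradiction in the reporting rules plus a gap in stated oversight. Protocol 6.1 and 6.2 give incompatible instructions for a serious Table 9 event, so SAE counts by arm may be incomplete. On either reading, such an event is outside the DMC's stated SAE review and outside REC and Sponsor notification.

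It is not a finding that harms go unrecorded: an arm difference in these complications would still be visible in the final complication tables. Nor does it extend to reoperation as such, which Table 9 does not list. The number affected is unknown. A reader might take about 53 as the number of SAEs bypassing the system, but that figure applies the highest cited literature re-repair rate to all 310 participants and is not a count of serious events. The conclusion does not depend on it. It rests on the wording of 5.6.4, 6.1, 6.2 and Table 9, and on the assumption that the DMC charter does not already close the gap. It is worth correcting because the remedy is cheap and follows the logic already in 6.2.

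**What to change.** Reconcile Protocol 5.6.4, 6.1, 6.2 and Table 9 with SAP Table 27:

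- In 6.1, limit the exemption to Table 9 events that meet no seriousness criterion.
- State that a Table 9 event meeting a seriousness criterion and the relatedness filter is recorded on the SAE form within the existing 24-hour limit and marked expected. No expedited REC report would follow, since 6.2 already reserves that for unexpected related SAEs.
- In 5.6.4, state that Table 9 complications are given to the DMC by arm at each meeting.
- Keep the expectedness rows in SAP Table 27, which would then match what is collected.

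The cost is a wording amendment and some additional SAE forms from sites. SAP Appendix C shows that recruitment was already under way, so complications already recorded would need checking against the seriousness criteria if the SAE tables are to be on one footing throughout. Nothing here alters treatment or the primary analysis.
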